4.2.2 NUMBER OF PARTICIPANTS

Participants will be recruited using CORE records and advertising approved by the UW Office of Research Ethics. Up to 55 eligible participants may be dispensed with study products, with a target of 40 participants completing the study. Informed consent will be obtained for all participants prior to their enrolment in the study (Appendix 1).

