4.4.7 STUDY EXIT

The Study Exit form must be completed when a participant exits the study. This will occur either at study completion or if the participant is discontinued from the study at another time. A Study Exit form must be completed for all participants who have been allocated a study ID number. Post-study follow-up visits will be scheduled if the investigator determines this is necessary and the exit form will be signed after the last follow-up visit.

At the Study Exit Visit the following details are required:

- Visual acuity with habitual lenses, spectacles or refraction (logMAR);
 - If the VA at the Exit Visit is two or more lines worse than at baseline, the investigator will be required to provide an explanation and complete an adverse event form.

• Post-study follow-up requirement (Y/N): If yes, the reason and date of the follow-up visit must also be recorded.

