8 DISCONTINUATION FROM THE STUDY

Participants may be discontinued at the discretion of the investigator in consideration of participant safety or protocol compliance, or at discretion of the participant. Participants discontinued from a study will be reimbursed \$20 per hour for their active involvement in the study (including the initial screening visit). Upon discontinuing, a participant will be offered the option of their data being withdrawn from future statistical analysis. The following is a list of possible reasons for discontinuation from the study:

- Screening failure: Participants will be discontinued if they do not meet the inclusion and exclusion criteria outlined in section 4.2.3.
- Unacceptable performance with products to be used in study: Participants may be discontinued if they are unable to achieve acceptable comfort and /or vision with the study products.
- Positive slit lamp finding: Participants may be permanently discontinued from the study depending on the severity of the condition and on the judgement of the investigator.
- Adverse event: If a participant experiences an adverse event during the study they may be discontinued based on the clinical judgement of the investigator.
- Symptoms: If the participant has persistent symptoms they may be discontinued based on the clinical judgement of the investigator.
- Disinterest, relocation or illness: The participant may choose to discontinue due to reasons within or beyond their control.
- Violation of protocol or non-compliance: The participant will be discontinued if they are unable or unwilling to follow the protocol specified visit schedules and/or study procedures.
- Instillation of topical ocular medication: The participant will be discontinued if they elect to use a
 topical ocular medication during the study unless that topical ocular medication is prescribed for a
 limited duration (less than two weeks) to treat a transient condition; in this case the participant
 may remain an active participant (at the discretion of the investigator) after stopping topical ocular
 medication following resolution of the ocular condition).
- Lost to follow-up: The participant will be discontinued if they cannot be contacted and do not return for a final exit visit, and if the investigator has made a reasonable effort to contact the participant for a final study visit.
- Premature termination of the study by CORE or the Office of Research Ethics at the University of Waterloo.

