10 STATISTICAL ANALYSIS AND DATA MANAGEMENT

10.1 STATISTICAL ANALYSIS

All data will be analyzed by CORE at the University of Waterloo. Unmasked data analysis will be conducted using Statistica 13 or later. Descriptive statistics will be provided on information regarding baseline variables (age, sex, refractive error distribution, etc.). For data collected on each eye individually (e.g. biomicroscopy), results of the right eye will be reported unless a difference between right eye and left eye is found. Table 3 lists the primary and other outcome variables and anticipated statistical procedures. All data will be tested for normality of distribution using Shapiro-Wilk tests. Statistical significance will be set at 5%. Superiority testing for the primary outcome variable (i.e. VAS ratings for CL-related discomfort and dryness at 12–weeks vs baseline) will be performed, using a superiority margin of 10 units on the 100-point scale. Additional statistical testing may be applied as required.

Table 4: Statistical procedures

Variable	Analysis	Statistical test
CLDEQ-8 score,	Descriptive statistics	Mean, Standard Deviation
 VAS ratings, Pre-lens non-invasive tear breakup time (PLNITBUT), bulbar and limbal redness, tear inflammatory markers; 	Effect of time on the outcome variables (Comparison between visits)	RMANOVA/MANOVA Mauchly's test of sphericity Huynh-Feldt p values Tukey HSD post hocs Paired t-test
Safety measures (biomicroscopy, visual acuity.)	Descriptive statistics Effect of safety and exploratory variables over time	Mean, Standard Deviation RMANOVA/MANOVA Mauchly's test of sphericity Huynh-Feldt p values Tukey HSD post hocs Paired t-test

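### The named primary analysis leaves out everyone without a Day 84 rating, while participants may be discontinued for poor comfort, persistent symptoms or adverse events, so the single-arm estimate risks bias toward benefit

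*Combined protocol and SAP*

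**What the plan says.** The primary outcome (section 2) is the VAS rating of contact-lens discomfort and dryness at 12 weeks against baseline. Section 10.1 adds a superiority test "using a superiority margin of 10 units on the 100-point scale" at a 5% level, without saying whether that is one- or two-sided. In Table 4 the VAS row, under "Effect of time on the outcome variables (Comparison between visits", lists repeated-measures ANOVA or MANOVA, Mauchly's test and "Huynh-Feldt p values Tukey HSD post hocs Paired t-test". The safety row carries the same list. I found no analysis population, missing-data rule or sensitivity analysis in the document.

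On leaving the study, section 8 says:

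- "Participants may be discontinued if they are unable to achieve acceptable comfort and /or vision with the study products"
- "If the participant has persistent symptoms they may be discontinued based on the clinical judgement of the investigator"
- "If a participant experiences an adverse event during the study they may be discontinued based on the clinical judgement of the investigator"

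It also lists reasons that need not relate to symptoms, such as relocation or disinterest, and it lets those who leave withdraw their data from analysis. Discontinuations and their reasons go into the final report. At study exit, section 4.4.7 requires "Visual acuity with habitual lenses, spectacles or refraction (logMAR" and a record of any follow-up needed; no VAS rating is listed. Section 4.2.2 gives the numbers: "Up to 55 eligible participants may be dispensed with study products, with a target of 40 participants completing the study".

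**The concern.** A paired t-test of baseline against Day 84 needs both ratings. Classical repeated-measures ANOVA needs every visit in the model, so it also drops anyone who missed Day 14 or Day 42, although that need not affect the paired test. The primary result is therefore a completer result.

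Two of the permitted reasons for leaving, unacceptable comfort and persistent symptoms, are close to what the primary VAS measures. Adverse events that bear on comfort are foreseeable: section 6 cites eye irritation in 18%, eye pain in 13% and instillation site reactions in 12% of earlier dry-eye participants, mostly mild and transient. If those who benefit less are more likely to leave, the completers' mean improvement is too high as an estimate for everyone treated, and that mean is what is compared with 10 units. In a single-arm study (section 4.1.2) no comparator suffers the same selection. Section 4.2.1 says that the data may be used to size later studies, so an inflated change could carry forward.

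**Working it through.** **Inputs from the document.** Up to 55 dispensed, 40 targeted to complete, margin 10, level 5%. The largest loss compatible with both numbers is 15/55 = 27.3%. Section 4.2.1 gives no effect size, SD or power, so the 40 cannot be reproduced.

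**Assumed inputs.** SD of change 25; correlation rho between staying and improving 0.2, 0.3 or 0.5; true mean improvement in all 55 exactly 10; 5, 10 or 15 leave.

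**Step 1: overstatement.** With p the proportion leaving and z = Φ⁻¹(p), the completers' mean exceeds the overall mean by rho × 25 × φ(z)/(1 − p). For 15 leaving, z = −0.605, φ(z) = 0.332 and 0.332/0.727 = 0.457. At rho 0.5 this is 0.5 × 25 × 0.457 = 5.7 units.

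**Step 2: chance of wrongly exceeding the margin.** This comes from the noncentral t with n − 1 degrees of freedom and noncentrality rho × factor × √n. The SD cancels, so these chances do not depend on it.

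| Leave | n | Factor | Overstatement, rho 0.2 / 0.3 / 0.5 | Chance, one-sided 2.5% | Chance, one-sided 5% |
|---|---|---|---|---|---|
| 5 | 50 | 0.180 | 0.9 / 1.35 / 2.25 | 4.4 / 5.6 / 9.1% | 8.2 / 10.2 / 15.4% |
| 10 | 45 | 0.323 | 1.6 / 2.4 / 4.0 | 6.2 / 9.3 / 18.4% | 11.2 / 15.7 / 28.1% |
| 15 | 40 | 0.457 | 2.3 / 3.4 / 5.7 | 8.1 / 13.3 / 29.1% | 14.1 / 21.4 / 41.1% |

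**Step 3: a second route without a correlation.** Suppose that leavers average zero change and the mean over all 55 is 10. The completers then average 10 × 55/n, which is 11.0, 12.2 or 13.75 when 5, 10 or 15 leave. At 13.75 with n = 40, the paired test exceeds the margin with probability 0.34, 0.21, 0.15 or 0.12 for SD 15, 20, 25 or 30 (nominal 0.025), or 0.46, 0.32, 0.24 or 0.19 (nominal 0.05).

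**Step 4: does a mixed model help?** Simulation with 55 dispensed, visit SD 25, between-visit correlation 0.5, true improvement 10 and 4,000 runs (all assumed):

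| What dropout depends on | Leave | Completers | Mixed model | Zero change for leavers |
|---|---|---|---|---|
| Observed Day 14/42 improvement, logit slope 0.75 or 1.5 per 25 units | 5 | 10.8 or 11.5 | 9.9–10.1 | – |
| Same | 15 | 12.6 or 14.1 | 9.9–10.1 | – |
| Unseen Day 84 change, slope 0.75 | 5 | 11.7 | 11.1 | 10.7 |
| Same | 15 | 15.1 | 13.4 | 10.9 |

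In the unseen case the model removes about a third of the bias: (11.7 − 11.1)/1.7 = 35% and (15.1 − 13.4)/5.1 = 33%. When 15 people leave before Day 14 because of their response at that time, a similar simulation (same SD and correlation, slope 0.75) gave 12.7 for completers and 11.5 for the model.

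**The case against.** The strongest reply has four parts.

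- **Target.** Sections 2 and 3 ask about change after 12 weeks of use, and section 4.2.2 aims for 40 completers. In a pilot, a completer contrast answers a defensible question, and it overstates only if the target is everyone treated. This stands in part: the document states no target population. A formal test against a margin still needs a stated population.
- **Size.** No dropout rate, SD or correlation is given, 15 is a ceiling, and section 8 says that participants may be discontinued for these reasons, not that they must be. At rho 0.3 the bias is 1.35, 2.4 or 3.4 units, below one standard error of the mean each time (25/√n = 3.5, 3.7, 4.0). All of this stands and limits how strongly the point can be put.
- **Remedy.** A mixed model cannot fully correct for dropout driven by unseen Day 84 outcomes or by very early leaving, and it lacks any data that leavers withdraw. This also stands. In each case simulated the model was nearer the truth than the completers' mean, and the remaining gap is the reason for the sensitivity analysis.
- **Existing safeguards.** Day 14 and Day 42 ratings are separate outcomes, an early-exit rating is not ruled out, section 10.1 allows additional testing, and discontinuations are reported. These make attrition visible but do not say in advance how the primary estimate handles it.

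**Conclusion.** The point holds as a risk of bias toward benefit, not as a demonstrated bias. The document alone shows that the named methods use nobody without a Day 84 rating, that outcome-related reasons for leaving are permitted, and that nothing states how missing ratings are handled. The direction depends on poorer responders leaving more often; the size depends on the assumed correlation and number lost, and in units also on the assumed SD. Over the ranges used, the overstatement runs from 0.9 to 5.7 units against a margin of 10. A nominal 2.5% chance of wrongly exceeding the margin becomes 4% to 29%, and a nominal 5% chance becomes 8% to 41%. The upper ends need both the largest loss and the strongest correlation. With dropout unrelated to outcome, the overstatement is zero. The plan should be changed because the better analysis uses ratings already collected; my confidence is medium because the loss to expect is unknown.

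**What to change.** In section 10.1:

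1. Define the primary analysis set as all participants dispensed Xiidra who have a baseline VAS.
2. For each of discomfort and dryness, fit a mixed model for repeated measures to all available ratings at V2 to V5, with visit as a fixed effect and an unstructured covariance. Test the V5 − V2 contrast against the 10-unit margin. State whether one or both ratings must clear it.
3. Say that this model assumes data missing at random. Add one pre-stated sensitivity analysis that gives zero change to participants without a V5 rating.
4. Keep the completer repeated-measures ANOVA and paired t-test as supportive.
5. Report how many participants withdrew their data under section 8, leaving that option and the discontinuation rules as they are.

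The cost is a few sentences, a little more analysis and a check that the named software fits the model. No visits, participants or consent wording are added. The reported improvement will probably be smaller. The zero-change analysis understates the effect if leaving is unrelated to outcome (10 × 40/55 = 7.3 for a true 10 when 15 leave), so it should serve only as a sensitivity analysis.

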4.5.8 SLIT LAMP BIOMICROSCOPY

The participant will be seated behind a slit lamp and the following will be assessed:

Cornea:

Any current or past corneal observations (such as infiltrates, old scars, etc) will be documented at each visit.

Corneal and conjunctival staining

A sodium fluorescein strip, wetted with a few drops of saline, will be applied to the superior bulbar conjunctiva of both eyes. Staining will be graded using the Efron scale (0 to 4, 0 = normal) while viewing with cobalt blue light through a Wratten no. 12 barrier filter.

Palpebral conjunctival hyperemia and roughness

The redness and roughness of the upper and lower eyelids (tarsal plate zone 2) will be assessed using the EFRON Grading scale (0 to 4, 0 = normal/ uniform satin appearance).

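### Table 4 analyses slit lamp grades and visual acuity only through averages and plans no count of participants who worsen

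*Combined protocol and SAP*

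**What the plan says.** Table 4 in section 10.1 has one row for "Safety measures (biomicroscopy, visual acuity", with two analyses: descriptive statistics (mean and standard deviation) and "Effect of safety and exploratory variables over time". The second lists RMANOVA/MANOVA, Mauchly's test, Huynh-Feldt p values, Tukey HSD and the paired t-test. On the test level, section 10.1 says "Statistical significance will be set at 5" per cent; it does not state sidedness for safety tests. For measurements taken on each eye, right-eye results are reported unless the two eyes are found to differ. What counts as a difference is not defined. Further tests are allowed, but none is named.

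The biomicroscopy variables are bounded grades. Section 4.5.8 states "Staining will be graded using the Efron scale (0 to 4, 0 = normal"), and gives the same range for palpebral redness and roughness.

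Elsewhere the protocol looks at the individual. Section 8, on slit lamp findings, says "Participants may be permanently discontinued from the study depending on the severity of the condition". Section 4.4.7 requires an explanation and an adverse event form when acuity at exit is at least two lines below baseline.

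On numbers, section 4.2.2 says "Up to 55 eligible participants may be dispensed with study products, with a target of 40 participants completing the study".

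**The concern.** The safety question for a slit lamp grade is usually whether a few people get clearly worse, not whether the average moves. On a scale bounded at 0, a few large rises among many unchanged values shift the mean only slightly and inflate the standard deviation at the same time, so a mean-based test has little chance of flagging them. Section 8 judges findings by their severity in the individual, and section 4.4.7 sets an individual threshold for acuity, but Table 4 carries neither idea into the analysis. The right-eye default adds to this, because a change confined to the left eye need not appear in the reported results.

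At stake is how informative the safety section of the report will be. The study is single-arm and open-label (sections 4.1.1 to 4.1.3), so a p-value for change over time says little about the drop. How many participants worsened, and by how much, is more useful.

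**Working it through.** The plan states no safety power or detectable safety change, so there is no figure of its own to reproduce.

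**Inputs from the documents.** n = 40 completers (section 4.2.2); grades 0 to 4 (section 4.5.8); 5% level, RMANOVA with Huynh-Feldt, Tukey HSD and paired t-test (section 10.1); visits V2 to V5, or V1 to V5 if screening is included (section 4.4).

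**Assumptions.** Two-sided testing; k participants worsen by three grades from V2 to V5; the others do not change.

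**Paired t-test, V5 against V2.** The mean change is 3k/n, and t = sqrt(k(n − 1)/(n − k)) on n − 1 degrees of freedom.

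- k = 3: mean 9/40 = 0.225, SD 0.800, t = sqrt(3 × 39/37) = 1.778, p = 0.083.
- k = 4: mean 12/40 = 0.300, t = sqrt(4 × 39/36) = 2.082, p = 0.044.

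For k = 3 the one-sided p is 0.042. With 35 or 55 analysed, three cases still give p = 0.083.

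**RMANOVA.** If the k participants share one time pattern and the rest are flat, F = k(n − 1)/(n − k), whatever the pattern. For k = 3, F = 3.162. The Huynh-Feldt epsilon is then 1/3 with four visits and 1/4 with five. The corrected degrees of freedom become 1 and 39, so p = 0.083, as for the t-test. Without the correction p is 0.027 (four visits) or 0.016 (five).

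**Tukey HSD, V5 against V2.** q = 0.225/sqrt(MSE/40), where MSE is the pooled RMANOVA error. For example, with four visits and worsening at V5 only, MSE = 6.75 × (3 − 9/40)/117 = 0.160, so q = 3.56 and p = 0.063. For k = 3:

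| Pattern of worsening | 4 visits | 5 visits |
|---|---|---|
| V5 only | 0.063 | 0.044 |
| V4 and V5 | 0.136 | 0.152 |
| V3 to V5 | 0.063 | 0.152 |
| Stepwise 1, 2, 3 | 0.021 | 0.035 |

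**Sensitivity of the paired t-test, k = 3.** If the other 37 all shift by +0.05, p = 0.035; by −0.05, p = 0.17. With random noise instead (SD of change 0.1 to 0.7), the test is significant in about 2% to 17% of simulated trials.

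**Right-eye rule.** If the three rises were in left eyes only and nothing else differed, a paired right-left comparison would involve the same 40 differences and again give p = 0.083. If a difference between eyes means a significant one, only right-eye results would then be reported.

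**The same data as a count.** 3/40 = 7.5%, exact (Clopper-Pearson) 95% CI 1.6% to 20.4%.

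**The case against.** The strongest reply is that individual worsening has other documented routes. Section 7 defines adverse events broadly, requires them to be collected on a form, and names corneal staining, infiltrates, limbal and bulbar injection and tarsal abnormalities as possible grounds for suspension. Section 8 allows discontinuation for a slit lamp finding and puts every discontinuation, with its reason, in the final report. Section 12 has the lead investigator review all adverse events. Section 4.4.7 has the two-line acuity rule. Section 10.1 leaves room for further tests, and even the planned SD of change (0.80 in the example) would hint at outliers. The study is also a pilot of marketed products in which safety is not a listed outcome.

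Much of this stands. A reader might infer that individual worsening would be hidden, or that a non-significant RMANOVA would be reported as no safety effect. The documents do not say either, and the routes above count against it. What remains is that those routes rest on judgement, none sets a biomicroscopy grade threshold, the acuity rule applies at exit only, and none feeds Table 4. Permission for extra tests commits to nothing.

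The example is also conditional. One-sided testing, the uncorrected F test, some Tukey patterns or a small common rise in the other participants would each make 3 of 40 significant.

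**Conclusion.** The point holds as a gap in the planned safety summary. Every procedure named for biomicroscopy and acuity concerns means, the right eye is the default, and no count of participants who worsen is planned. Under two-sided testing with no change in the others, 3 of 40 worsening by three grades gives p = 0.083 on the paired t-test and the Huynh-Feldt RMANOVA, and about 0.02 to 0.15 on Tukey. Four of 40 crosses 5% on the first two tests (p = 0.044). The assumption about the other participants is mine, as the documents give no grade distribution; section 4.2.3 admits mild staining and lid abnormalities, so baseline grades need not all be 0.

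A reader might go further and set the paired t for 5 of 40 (2.36) against a Tukey-size cut-off of about 2.61, inferring that even 12.5% would be missed. That does not follow. Tukey HSD after RMANOVA uses the pooled error, and with it 5 of 40 is significant in all eight patterns checked (p = 0.001 to 0.023).

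The primary comfort and dryness analysis is not affected.

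**What to change.** In Table 4, make the main safety summary a shift table of biomicroscopy grades from V2 to each follow-up visit. Add the number and percentage of participants whose grade rises by 1, by 2, or by 3 or more in either eye, and of those whose acuity is two or more lines worse (the protocol's own exit criterion), each with an exact 95% confidence interval. Keep means and SDs as secondary description, and do not base safety conclusions on RMANOVA p-values.

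All the data are already collected at these visits (Table 2). The cost is a few more table rows, with no change to procedures, visits or any clinical rule.

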10.2 DATA MANAGEMENT

Data from this study will be retained by CORE for a minimum of 25 years on a password-protected server. After 25 years, data will be disposed of in accordance with the guidelines laid out by the University of Waterloo.

At the completion of the study CORE may provide a copy of the study data to the funding agency, Novartis, when requested. Data will typically be sent using a secure file share system operated by the University of Waterloo called Sendit which uses 128bit (or 256bit) SSL encryption. This system provides a secure way to transfer files when email is not appropriate, whether because of file size, file type or concerns over security. Sendit includes features such as password protection, a restricted time period for download, IP logging and email notification of download. Files may be encrypted prior to transmission upon request. Using this method means that data files are only stored on University of Waterloo servers during the transfer.

